This study has been implemented to evaluate the efficacy and safety of Neutrolin[®] as a catheter lock solution (CLS) when used for the prevention of catheter-related bloodstream infection (CRBSI) in patients receiving hemodialysis (HD) for the treatment of End Stage Renal Disease (ESRD).

1.1 Objectives

The primary objective of this study is to demonstrate the efficacy and safety of Neutrolin[®] as a catheter lock solution (CLS) for prevention of catheter-related bloodstream infection (CRBSI) in subjects receiving hemodialysis (HD) for the treatment of End Stage Renal Disease (ESRD) when compared with heparin 4,000 USP Units/4 mL (1,000 USP Units/mL). The study will demonstrate whether Neutrolin[®] is superior to the active control heparin in reducing the incidence of CRBSI.

1.2 Study Design

This is a randomized, double-blind, active control, parallel-arm, multicenter study. Approximately 900 subjects will be randomized in a 1:1 ratio to receive either Neutrolin[®] or the active control heparin (Heparin sodium USP 1,000 units/mL, Benzyl alcohol 9.45 mg/mL and Sodium chloride 9.0 mg/mL) as a CLS. Neutrolin[®] or heparin will be instilled into central venous HD catheters at the discontinuation of all dialysis sessions and will be withdrawn prior to the initiation of the next dialysis session. All subjects will receive standard of care consistent with clinical practice guidelines recommended by the Kidney Disease Outcomes Quality Initiative (KDOQI) for the placement, care and use of central venous catheters (CVC) for HD therapy.

The primary endpoint is the presence or absence of a CRBSI (analysis will be made using the time to CRBSI). Subjects are to be followed from randomization (HD catheter will be in place prior to randomization) until occurrence of CRBSI, catheter removal, or the end of the study, whichever occurs first. The study has been designed to continue until approximately 56 subjects have experienced a CRBSI. It is expected that some subjects may be treated for 2 years or more.

1.3 Method of Assigning Subjects to Treatment Groups

Subjects will be randomized in a 1:1 ratio to receive either Neutrolin[®] or the active control heparin (1,000 USP units/mL) as a CLS. Permuted block randomization (centralized) will be utilized without additional stratification.

1.4 Blinding

This is a double-blind study. The sponsor, subjects and investigator staff will not have access to unblinded data (with the exception of sponsor staff required to be unblinded as needed to make safety reports to regulatory agencies) until the study is unblinded for the final study analysis. Prior to the final study analysis, the DSMB will have access to unblinded data as needed for their review. To maintain the double-blind nature of this study, the DSMB reports will be prepared by an independent statistical group that will not otherwise be involved with the study.

1.5 Sample Size

This trial has been designed to achieve 80% power for the comparison between treatment arms subject to the following specifications: testing will be conducted at a 2-sided overall 5% alpha level using the log-rank test, Neutrolin is associated with a 55% reduction in the risk of CRBSI relative to the control arm, a 1 to 1 ratio will be used for the allocation of subjects to treatment arms, and one interim analysis will be performed at the midpoint of the trial with adjustment of the alpha level using the method of Pocock. Fifty-six CRBSI events in total will be needed to achieve the desired power. The interim analysis will be conducted based on the first 28 CRBSIs. The total sample size is expected to be approximately 900 subjects.

2 Statistical Methods

2.1 Analysis Populations

Three analysis populations will be defined. These populations are

- Randomized Population – all subjects randomized. Subjects will be analyzed according to their allocated group determined by randomization.
- Full Analysis Population – all subjects randomized and receiving one or more doses of study medication. This population has been designed to be consistent with the intent-to-treat principle as the decision to begin treatment in this double-blind trial could not be influenced by knowledge of the assigned treatment (ICH-E9). Subjects will be analyzed according to their allocated group determined by randomization.
- Safety Population – all subjects taking at least one dose of study medication. Subjects will be analyzed according to the treatment they actually received. It is expected that the Safety Population will be identical to the Full Analysis Population.

2.2 Study Drug Dosing and Compliance

Study drug dosing will be assessed by calculating the duration of exposure, i.e., the length of time each subject received study drug, the total number of times drug was administered, the total number of vials administered, and the average dose. Study drug compliance will be assessed by calculating, at the subject level, the percentage of dialysis sessions at the study site at which the correct dosing was administered.

2.3 Study Endpoints

Primary Endpoint

CRBSI defined as one positive blood culture (other than for coagulase negative *Staphylococcus*, which requires a confirmatory culture) from:

1. a peripheral site or blood line sample or
2. either the arterial or venous catheter hub (or the venous or arterial dialysis circuit blood lines if on dialysis)

in a patient with no other apparent source of bloodstream infection other than the hemodialysis catheter, as assessed by the Clinical Adjudication Committee (CAC).

Secondary Endpoints

- Catheter Removal: Catheter removal for any reason during the follow-up period of the trial.
- Loss of Catheter Patency: Loss of catheter patency is defined as required use of a tissue plasminogen activating factor (tPA) or removal of the catheter because of dysfunction during the follow-up period of the trial.

2.4 Statistical Assessment of the Trial Objectives

2.4.1 Primary Endpoint Analysis

The primary analysis will be conducted using a log-rank test for the time to CRBSI at an overall 2-sided 5% alpha level. The null hypothesis is that there is no difference in the hazard rates of CRBSI over time between the two treatments. The time until CRBSI will be calculated as the number of days post randomization until the occurrence of a CAC-adjudicated CRBSI or the subject is censored. Subjects without a CRBSI will be treated as censored in this analysis if the catheter is removed for reasons other than CRBSI (e.g., catheter removed because no longer required) or follow-up is completed in the absence of CRBSI. Because an interim analysis for efficacy will be performed, the method of Pocock will be used to control the overall alpha level. Therefore, the nominal significance level at the interim and final statistical analyses for the primary efficacy endpoint will be 0.0294.

The primary analysis will be based upon the Full Analysis Population. While testing will be based upon the log-rank test, the estimated treatment effect will be the difference between treatment groups in the incidence rate of CRBSI, calculated as the number of subjects with a CRBSI divided by the number of catheter-days of follow-up over subjects (follow-up will be based upon the same time as used for the log-rank test). The rates will be presented as the event rates per 1000 catheter-days with a 95% confidence interval for the purpose of comparison of rates between the treatments. This confidence interval will be derived assuming that the number of catheter-days until CRBSI follows an exponential distribution.

In the primary analysis of the primary endpoint, cases considered to be indeterminate by the CAC will be excluded. A sensitivity analysis will be performed in which cases considered to be indeterminate will be treated as CRBSI events.

2.4.2 Secondary Endpoint Analyses

Time until catheter removal for any reason and time to loss of catheter patency will be analyzed using similar methods as for the primary analysis in the Full Analysis Population. Loss of catheter patency is defined as required use of a tissue plasminogen activating factor (tPA) or removal of the catheter due to dysfunction. For these endpoints, subjects will be considered censored as of their final clinical assessment if the event of interest is not observed. Otherwise, the event time will be the number of catheter-days between randomization and the event. The fixed sequence testing procedure will be used for the comparison of the two treatments with respect to the efficacy endpoints. Therefore, the analysis comparing the two treatments for catheter removal for any reason will be formally conducted only if the analysis for the primary effectiveness endpoint yields a statistically significant result favoring Neutrolin®, and the analysis comparing the two treatments for loss of patency will be formally conducted only if the analysis for catheter loss for any reason also yields a statistically significant result favoring Neutrolin®.

In addition to basic descriptive statistics, the rates per 1000 catheter-days of follow-up will be presented for both endpoints. Also, the reason for catheter loss will be summarized by treatment group.

2.5 Study Day and Visit Windows

Study day is defined as

$$\text{Study Day} = \begin{matrix} \text{event date-randomization date} +1 & (\text{on or after the day of randomization}) \\ \text{event date-randomization date} & (\text{before the day of randomization}) \end{matrix}$$

The following data will be collected at each dialysis session (2 or 3 times per week) until study completion:

- weight
- vital signs (temperature, blood pressure, pulse, respiratory rate)
- exit site assessment
- mean blood flow (Qb)
- adverse event assessment
- interventions such as thrombolytic therapy
- CRBSI assessment
- concomitant medications

The following data will be collected monthly:

- weight
- vital signs
- hematology
- chemistry
- dialysis treatment adequacy assessment - Single pool Kt/V (Sp Kt/V)
- concomitant medications

For descriptive analyses that may require the assignment of visits to months (e.g., hematology graphs), assessments will be assigned to analysis months (every 4 weeks) based upon the date the assessment took place regardless of the CRF page completed. Assessments will be mapped to visits as outlined in Table 1. Should more than one assessment exist within a given visit window the value closest to the scheduled visit should be used (choose the later visit if equally close). For data collected at each dialysis visit, analysis windows will not be assigned, and the nominal visits (week/day) will be used for data display.

Table 1 Monthly Visit Windows

Visit	Start of Window	End of Window
Baseline	Date of informed consent	0
Month 1	1	41
Month 2	42	69

For subjects where the reference date is missing, the study day will also be missing.

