7.0 EFFECTIVENESS AND SAFETY VARIABLES

7.1 SCHEDULE OF ASSESSMENTS

The schedule of study visits and assessments is displayed in the following Schedule of Assessments Table:

Table 2. Study Flow Chart	Screening	Baseline Visit	Routine Dialysis Visits	Monthly Assessments ^c	Per protocol (when CRBSI suspected) ^b	Final Safety Visit
Study Assessments	Day -14 to 0 ^a	Day 1	Dialysis visits after day 1, though study completion	Every 4 weeks (+/- 5 days)		28 (+7) days following the removal of last IP dose
Informed consent	X					
Assess inclusion/exclusion criteria	X	X				
Randomization		X				
Investigational product Administration		X	X	X		
Demographics	X					
Medical and surgical history (including vascular access status)	X				Focused	
Medication history	X					
Physical exam	X				Focused	X
Vital signs (Temp, Pulse, Respiratory Rate)	X	X	X	X	X	X
Blood pressure (pre-and post-dialysis) ^l	X	X	X	X	X	X
Height	X					
Weight (pre-and post-dialysis) ^j	X		X	X		X
Blood Cultures ^d					X	
Serum pregnancy test ^e	X			X		X
Blood glucose, leukocyte count, CRP, and procalcitonin					X	
Hematology ^f	X			X		X
Blood chemistry ^g (including adjusted serum calcium and albumin)	X			X		X
spKt/V	X			X		
Dialysis prescription parameters ^j	X	X	X	X		
Dialyzer Blood Flow ^j	X	X	X	X		
Treatment Time ^j	X	X	X	X		
Interventions ^h	X	X	X	X	X	X
Assessment of Skin around catheter ⁱ	X	X	X	X	X	X
Adverse & clinical endpoint events		X	X	X	X	X
Concomitant medication ^k	X	X	X	X		X
Verify compliance with study product administration				X		

^a Some historical data earlier than Day -14 may be needed

^b Document primary endpoint

^c Visit to occur every 4 weeks concurrently with one of the dialysis treatment visits for the duration of subject participation in the

- study.
- ^d Blood cultures must be drawn if CRBSI is suspected
 - ^e Applies only to female subjects of child-bearing potential
 - ^f Hematology panel: complete blood count (CBC) with differential, platelets, and reticulocyte count (%)
 - ^g Blood chemistry panel: sodium, potassium, chloride, blood urea nitrogen (BUN), serum creatinine, aspartate aminotransferase (AST), alanine aminotransferase (ALT), alkaline phosphatase, bilirubin, adjusted serum calcium, serum albumin, carbon dioxide, and glucose
 - ^h Use of tPA or other thrombolytic treatments
 - ⁱ Assess skin around catheter for signs and symptoms of breakdown, infection (e.g. erythema, edema, induration, or discharge), and bruising

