7.1.5 Monthly Assessments (+/- 5 days)

The following assessments are to be conducted every 4 weeks (i.e. monthly), and will be conducted as a part of one of the regularly scheduled dialysis treatment visits that occur 3 times weekly:

- Weight (pre-and post-dialysis, in kg)
- Vital signs (before dialysis treatment; monthly assessment is concurrently collected at dialysis treatment visit)
- Blood pressure (pre and post dialysis)
- Blood sample for clinical laboratory assessments:
 - Hematology
 - Blood chemistry and liver function
 - Serum pregnancy test for women of childbearing potential
- Verify compliance with study product administration
- Verify and document dialysis prescription parameters
- Dialyzer blood flow
- Actual treatment duration
- Interventions
- Assess skin around catheter for signs and symptoms of breakdown, infection (e.g. erythema, edema, induration, or discharge), and bruising
- spKt/V
- Concomitant medications
- Adverse and clinical endpoint event assessment (concurrently collected at dialysis treatment visit).

7.1.6 Final Safety Visit (28 days, + 7 days after removal of last dose of investigational product)

This visit would be completed 28 days after the removal of the investigational product from the HD catheter at the scheduled final safety visit for each subject. Subjects will return to a standard of care CLS to be instilled into the HD catheter after the completion of dialysis at this visit. If there is any reason why the subject cannot attend this visit, then the subject assessment should be done in the dialysis unit. There is a +7-day window to allow convenient scheduling.

The following assessments are to be conducted:

- Physical Exam (NOTE: a physical examination may be conducted by an appropriately delegated sub-investigator or medically qualified personnel)
- Vital signs
- Blood pressure (pre and post dialysis)
- Weight (pre- and post-dialysis, in kg)
- Blood sample for clinical laboratory assessments
 - Hematology

- Blood chemistry
- Serum Pregnancy test
- Concomitant medications taken through the final study visit
- Assess skin around catheter for signs and symptoms of breakdown, infection (e.g. erythema, edema, induration, or discharge), and bruising
- Adverse and clinical endpoint event assessments
- Interventions – record use of thrombolytic therapy if required.

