3.8.3 Clinical Laboratory Tests

Descriptive statistics will be calculated for clinical laboratory tests (hematology, serum chemistry) at applicable visits. Where applicable, changes from baseline will be summarized by treatment group.

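### SAP 2.5 assigns laboratory values to months by date with no on-treatment limit, so off-lock Final Safety Visit samples enter on-lock monthly summaries and may attenuate or distort between-arm differences

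*SAP*

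**What the plan says.** SAP 2.5 opens the rule with its scope: "For descriptive analyses that may require the assignment of visits to months (e.g., hematology graphs"). For those analyses, "assessments will be assigned to analysis months (every 4 weeks) based upon the date the assessment took place regardless of the CRF page completed". It continues: "Assessments will be mapped to visits as outlined in Table 1". Table 1, as it reads in the text available, gives Month 1 as days 1 to 41 and Month 2 as days 42 to 69. If two values share a window, "Should more than one assessment exist within a given visit window the value closest to the scheduled visit should be used", with the later one taken in a tie.

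The Protocol's study flow chart (Table 2) places the Final Safety Visit at "28 (+7) days following the removal of last IP dose". Both that table and Protocol 7.1.6 list hematology and blood chemistry at the visit.

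SAP 3.8.3 says: "Descriptive statistics will be calculated for clinical laboratory tests (hematology, serum chemistry) at applicable visits". It adds changes from baseline where applicable. None of SAP 2.7, 3.8 or 3.8.3 restricts values to time on the study lock. Addendum 1.2 bases the primary safety analyses on data through the last patient's last visit. A limit does exist in addendum 1.1, last study drug dose plus 3 days, but only as a censoring date for the efficacy endpoints.

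**The concern.** The visit page on the CRF is the plain marker that separates a final-visit sample from a monthly one, and the SAP rule sets it aside. A subject at the Final Safety Visit has been off the study lock for four to five weeks. Suppose the lock is last removed on Day 60. The final sample is then drawn on Day 88 to 95 and, if 28-day windows continue, is filed under Month 3 (days 70 to 97) beside values from subjects still on the lock.

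Laboratory assessment is a named safety objective (Protocol 3.2). SAP section 4 drops the count of subjects with abnormal laboratory results that the protocol had promised, so the by-visit descriptive summary carries more of the laboratory evidence. A modest mean shift that no investigator would report as an adverse event would have to be seen there.

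**Working it through.** **1. Reproducing the plan's windows.** With visits every 4 weeks, the scheduled days are 28 and 56. Their midpoint is (28 + 56)/2 = 42, the stated start of Month 2. Month 2 runs from 56 − 14 = 42 to 56 + 13 = 69, which is 28 days. Table 1 reproduces. I assume the same 28-day pattern after Month 2; later rows may be missing from the text available.

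**2. Does the closest-value rule protect the month?** Monthly visits are allowed ±5 days. The earliest on-lock visit for month k is day 28k − 5. A final visit for that subject is at least 28 days later, so on day 28k + 23 or after. The window ends on day 28k + 13. The two can never share a window, the tie-break is never reached, and the off-lock value stands alone in its month. (The Early Withdrawal Visit of Protocol 7.1.7 also draws blood; it is not modelled here.)

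**3. Off-lock share of a month's values.** Assumptions, none from the documents: time on lock is exponential with mean m days, and a fraction a attend the final visit. From the protocol, the final visit falls 28 to 35 days after lock removal, midpoint 31.5.

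- *Later months.* On-lock values at scheduled day t are proportional to exp(−t/m). Final visits within 14 days of t come from stops between t − 45.5 and t − 17.5. Relative to on-lock values, r = exp(45.5/m) − exp(17.5/m), and the share is a·r/(1 + a·r).
 - m = 100: r = 1.576 − 1.191 = 0.385. Share 0.385/1.385 = 28% at a = 1; 0.269/1.269 = 21% at a = 0.7.
 - m = 365: r = 1.133 − 1.049 = 0.084. Share 7.7% at a = 1; 5.5% at a = 0.7.
- *Month 1.* A final visit by day 41 needs a stop by day 41 − 31.5 = 9.5. Off = a·[1 − exp(−9.5/m)]; on = exp(−28/m).
 - m = 100, a = 1: 0.091/(0.091 + 0.756) = 10.7%.
 - m = 365, a = 0.7: 0.018/(0.018 + 0.926) = 1.9%.

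A simulation of 100,000 subjects, with scattered visit days and the SAP's selection rule, agrees. It found no final visit sharing a window with an on-lock monthly visit.

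| Mean days on lock | Month 1, 100% / 70% attend | Later months, 100% / 70% attend |
|---|---|---|
| 100 | 10% / 8% | 28% / 21% |
| 200 | 5% / 4% | 14% / 10% |
| 365 | 3% / 2% | 8% / 5–6% |

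With a mean of only 60 days the shares would be higher: 19% / 14% in Month 1 and about 44–45% / 35–36% in Months 2 to 6.

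**4. Effect on a between-arm difference.** Write μ for the on-lock mean, ν for the off-lock mean and s for the off-lock share in each arm. The observed difference is [(1 − s_N)μ_N + s_N·ν_N] − [(1 − s_H)μ_H + s_H·ν_H], with N for Neutrolin and H for heparin.

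- Effect fully reverses, equal shares (ν_N = ν_H = μ_H): the difference becomes (1 − s)(μ_N − μ_H). With the shares for means of 100 to 365 days, 90–98% of the true difference remains in Month 1 and 72–95% later.
- Effect persists past 28 days (ν = μ in each arm): no attenuation.
- No lock effect (μ_N = μ_H = μ): the difference is s_N(ν_N − μ) − s_H(ν_H − μ), which is not zero if leavers differ by arm. The design expects this to some degree. With a 55% risk reduction and equal follow-up, 56 CRBSI events split as 56 × 0.45/1.45 ≈ 17 against 56/1.45 ≈ 39, and those subjects also reach a final visit. CRBSI leavers are few overall, however: 56/900 ≈ 6%.

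**The case against.** The strongest reply is that the rule is conditional. It covers analyses that need visits assigned to months, and SAP 3.8.3 speaks only of applicable visits. The Final Safety Visit has its own column in the protocol's flow chart, so a separate row for it is compatible with the text. That stands as far as it goes: the SAP does not say that every laboratory table pools these values. But the rule's own example is hematology graphs, so laboratory data are in scope. Wherever the rule is applied, it ignores the visit page, and no separate display is specified.

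A reader might infer that vital signs are pooled in the same way. The documents do not establish that. SAP 2.5 lists vital signs among data collected at each dialysis session, for which it says: "For data collected at each dialysis visit, analysis windows will not be assigned, and the nominal visits (week/day) will be used for data display". It also lists them among monthly data, and SAP 3.8.4 summarises them for the monthly visit. The SAP is ambiguous here.

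A reader might also infer that any laboratory signal is diluted or hidden. That goes too far. Dilution needs an effect that reverses off the lock, which no passage addresses, and the distortion could run in either direction. Clinically relevant laboratory changes are recorded as adverse events (Protocol 7.4.3) and reach tables that do not use month windows. Laboratory summaries are descriptive, without routine testing (SAP 2.7). Each subject contributes at most one final-visit value, and Month 1 is much less affected than later months.

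**Conclusion.** The point holds for laboratory data summarised by analysis month. Following SAP 2.5 as written places samples taken 28 to 35 days off the study lock among on-lock values, and nothing in the SAP or addendum prevents it. That rests on the text and on the window arithmetic in step 2, given that monthly visits keep their ±5 days and 28-day windows continue.

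The size is conditional. For mean lock times of 100 to 365 days and 70 to 100% attendance, the off-lock share is about 2–10% in Month 1 and 5–28% later. These inputs are assumptions, because the documents report neither lock time nor attendance. Attenuation by the same fraction follows only if the effect fully reverses and the share is equal in both arms. The primary and secondary efficacy analyses are untouched. The change is still worth making, because the abnormal-value counts have been dropped and the repair is small.

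**What to change.** In SAP 2.5, limit the date-based month windows for laboratory data to assessments on or before last study drug dose plus 3 days, and carry this into the safety analyses of addendum 1.2. Summarise the Final Safety Visit as its own post-treatment visit. The off-lock share of each month then becomes zero under the same definition. State also whether this applies to the monthly vital-sign summary.

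The cost is slightly fewer values in each month and one more table column. Dose dates and the visit page are already collected, so no new data are needed.

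Separately, the protocol should be reconciled on which lock is in place before the Final Safety Visit. Table 2 dates the visit from removal of the last dose. Section 7.1.6 speaks of returning to a standard-of-care lock at that visit. Section 7.1.7 has a non-investigational lock used once a subject withdraws early. Which arrangement is intended is for the sponsor to settle; the passages need to agree so that off-lock time is well defined.
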